The treatment variable was exposure to the BCC intervention (yes/no). The covariates included physical activity, obesity, dietary habits, lifestyle factors, and socio-demographic characteristics. Physical activity was classified according to WHO guidelines (7) as: (i) sedentary: light-intensity activities; (ii) active: moderate-intensity activities for 150–300 minutes per week; and (iii) athlete: vigorous-intensity activities for 75–150 minutes per week. Obesity was assessed using body mass index (BMI, kg/m²) and categorized according to WHO Asian-specific cut-offs (8): (i) underweight (<18.5), (ii) normal weight (18.5–22.9), (iii) overweight (23.0–27.5), and (iv) obese (>27.5). Dietary information was collected using a five-day 24-hour recall method, and dietary diversity score (DDS) was calculated following FAO guidelines (9) . Lifestyle-related covariates included food cravings for high-fat or sweet foods (10), skipping breakfast, sleep duration, bedtime and caffeine intake (11). Socio-demographic variables included family history of menstrual disorders, age at menarche, marital status, and participants' residence as well as parental educational and occupational status.

Data were collected through interviewer-administered, culturally adapted, and validated Bengali-questionnaires. Descriptive statistics summarized baseline characteristics. Group differences were tested using chi-square and t-tests. Propensity scores were estimated using logistic regression, and covariate balance post-matching was evaluated using standardized mean differences (SMD <10%). Intervention effects were analyzed using conditional logistic regression on the matched sample, and logistic regression (bivariate/multivariate) on the unmatched sample. Sensitivity analyses included covariate balance diagnostics, estimation of average treatment effects (ATE/ATT), and Bayesian logistic regression with log Bayes factor.

This study complies with U.S. regulatory requirements for clinical trial registration and reporting under 42 CFR Part 11. The responsible party confirms that all submitted information is complete and accurate, and that the study protocol, statistical analysis plan (SAP), and informed consent form (ICF) reflect the approved trial objectives and design.

Participant flow

Recruitment details

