To evaluate the impact of the BCC intervention on reducing dysmenorrhea, key covariates were balanced between groups using propensity score matching. These included physical activity level, BMI, minimum dietary diversity (MDD score ≥ 5), food cravings for high-fat and sweet foods, breakfast skipping, sleep duration, caffeine intake frequency, family history of menstrual disorders, age at menarche, marital status, father's and mother's educational status, and mother's occupation. These balanced covariates (13 covariates) were included in the regression models and in the estimation of both the average treatment effect (ATE) and the average treatment effect on the treated (ATT).

Additionally, to assess the effectiveness of the intervention on PMS and MI outcomes, propensity score matching was used to achieve balance in key baseline covariates between the intervention and control groups. The matched covariates included physical activity level, BMI (kg/m^2), minimum dietary diversity (MDD score ≥ 5), food cravings for high-fat and sweet foods, breakfast skipping, sleep duration, age at menarche, and participants' residence. These variables (8 covariates) were subsequently adjusted for in the estimation of treatment effects.

Table 6. Baseline characteristics of participants by defined study measures

Baseline measure title (Study-specific measure)	Study-specific baseline measure title(s)	Baseline measure description	Measure type	Measure of dispersion	Category title	Unit of measure
Physical activity	Physical activity level	Categorized per WHO recommendations based on weekly activity intensity: sedentary (with little or no activity), active (moderate, 150–300 min/week) and athlete (vigorous, 75–150 min/week). Active and athlete were merged during analysis	Count of participants	Not applicable	Sedentary/ Active and athlete	Participants
Body mass index (BMI)	BMI (Kg/m ²)	Classified using WHO cut-offs for Asian populations, such as underweight (<18.5), normal (18.5–22.9) and overweight/obese (≥23.0). Overweight and obese categories were merged.	Count of Participants	Not applicable	Underweight / Normal / Overweight and obese	Participants

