
Statistical Analysis Plan (SAP)

Statistical analysis overview

Statistical analyses were conducted to evaluate the impact of the BCC intervention on three binary outcomes: dysmenorrhea, PMS, and IMC. Categorical variables were summarized as frequencies and percentages and analyzed using the chi-square (χ^2) test. Continuous variables were presented as means with standard deviations and compared using independent t-tests. To adjust for potential baseline imbalances between the intervention and control groups, propensity score matching (PSM) was carried out using logistic regression. A 1:1 nearest-neighbor matching algorithm was applied with a caliper width of 0.01 and without replacement. Post-matching covariate balance was assessed using standardized mean differences (with a bias threshold of <10%) and chi-square tests. The primary analysis of intervention effects was conducted using conditional logistic regression on the matched sample. To validate the findings, bivariate and multivariate logistic regression analyses were also performed on the unmatched dataset. Additionally, sensitivity analyses were conducted to ensure the robustness and consistency of the results, including covariate balance diagnostics, estimation of the average treatment effect (ATE) and the average treatment effect on the treated (ATT), and Bayesian logistic regression on the matched sample.

Comparison group selection

1. Intervention Group (received BCC module)
2. Control Group (did not receive BCC module)

Type of statistical test: Superiority

- Comments: The analyses were designed to assess whether the BCC intervention group had superior outcomes compared to the control group using fixed-effect models on matched pairs. Power calculations were based on expected reductions in outcome prevalence.

Statistical test of hypothesis

Conditional logistic regression was used to estimate the odds of binary outcomes between intervention and control groups after matching.

- P-Value: < 0.05
- Comments (P-Value): A p-value < 0.05 was considered statistically significant. No adjustments for multiple comparisons were made. Results were considered statistically significant at $p < 0.05$.

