- Method: Chi-squared, t-test, regression (logistic), conditional logistic regression
- Comments (Method): Pre- and post-PSM tests used Pearson's chi-square; conditional logistic regression applied to matched data; bivariate and multivariate logistic regression used for robustness checks

Method of Estimation

- Estimation Parameter: Odds Ratio (OR)
- Estimated Values: Reported as crude odds ratios (COR) and adjusted odds ratios (AOR). Coefficient value was used to estimate ATE and ATT (Table 11).
- Confidence Interval Level: 95%
- Number of Sides: 2-sided
- Lower and upper limit: Reported per outcome (see Table 11)

- Parameter Dispersion Type: Standard error of the mean
- Estimation Comments: Odds ratios compared the intervention group (numerator) to the control group (reference) for menstrual outcomes. Odds ratios reflect the likelihood of menstrual outcomes in the intervention group relative to the control group. ATE and ATT were also estimated using PSM.

Table 11. Estimated odds ratios from bivariate and multivariable (before matching) as well as conditional (after matching) and logistic regression models assessing the impact of the BCC module on menstrual health outcomes

Outcomes	Before matching		After matching
	COR (95% CI)	AOR (95% CI)	AOR (95% CI)
Dysmenorrhea	0.07 (0.04, 0.11)***	0.13 (0.06, 0.26)***	0.13 (0.05, 0.34)***
Premenstrual syndrome	0.07 (0.04, 0.11)***	0.13 (0.07, 0.23)***	0.12 (0.06, 0.27)***
Menstrual Irregularity	0.12 (0.07, 0.20)***	0.26 (0.14, 0.48)***	0.21 (0.09, 0.45)***

* Indicated chi square value define the level of significance i.e. * $p < 0.05$, ** $p < 0.01$, *** $p < 0.001$

Other statistical analysis

Additional scientifically appropriate analyses were conducted to ensure robustness and validity of the findings:

1. **Propensity Score Matching (PSM):** PSM was used to control for baseline differences between the intervention and control groups. Participants were matched 1:1 using nearest-neighbor matching with a caliper width of 0.01 and without replacement. Covariate balance was assessed using standardized mean differences (bias <10%) and post-matching chi-square tests.

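### Does it matter that no section states which covariates the primary conditional logistic model contains?

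*Combined protocol and SAP*

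**What the plan says.** The SAP (Statistical analysis overview) fixes the primary method: "The primary analysis of intervention effects was conducted using conditional logistic regression on the matched sample". Statistical test of hypothesis adds only that "Conditional logistic regression was used to estimate the odds of binary outcomes between intervention and control groups after matching". Neither lists model terms.

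Covariates appear in the protocol section Baseline Measure Information, separately by outcome:

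- For dysmenorrhea it names 13 variables and says "These balanced covariates (13 covariates) were included in the regression models".
- For PMS and MI it names 8 and says "These variables (8 covariates) were subsequently adjusted for in the estimation of treatment effects".

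Table 11 heads the after-matching column as an adjusted odds ratio. Its title, however, reads "Estimated odds ratios from bivariate and multivariable (before matching) as well as conditional (after matching) and logistic regression models", which ties the multivariable model to the unmatched data. Three other places do the same:

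- Protocol, Detailed description: "Intervention effects were analyzed using conditional logistic regression on the matched sample, and logistic regression (bivariate/multivariate) on the unmatched sample".
- SAP, Statistical analysis overview: "bivariate and multivariate logistic regression analyses were also performed on the unmatched dataset".
- SAP, Comments (Method): "conditional logistic regression applied to matched data; bivariate and multivariate logistic regression used for robustness checks".

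**The concern.** Two readings of the primary model coexist. In the first, it carries the full covariate list, as the dysmenorrhea sentence and the column heading suggest. In the second, it contains exposure only and the adjustment comes from the matching, as the wording about unmatched data suggests. For PMS and MI the first reading rests mainly on the column heading, because the treatment effects mentioned there may simply be those of Table 12.

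The choice is not cosmetic. In a 1:1 conditional model only pairs with different outcomes carry information. Many covariates on few such pairs push a non-null odds ratio away from 1, here towards a larger apparent benefit. A reader who takes the full-list reading would have reason to doubt the size of the headline effects.

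**Working it through.** **1. Parameters.** The named lists count to 13 and 8, as stated. BMI has three categories and so needs two terms; exposure adds one. Dysmenorrhea: 13 + 1 + 1 = 15. PMS and MI: 8 + 1 + 1 = 10. With 98 pairs, there are at most 98/15 = 6.5 or 98/10 = 9.8 pairs per parameter.

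**2. What a full-list fit would do.** This was simulated with a true odds ratio of 0.20, fixed discordant counts and 2,000 replicates. Covariates were drawn at the total-column frequencies of Tables 7A and 7B, independent within pairs and without effect on the outcome. Medians are over converged fits.

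| Discordant pairs | Median OR, 15 parameters | Median OR, 10 parameters |
|---|---|---|
| 98 | 0.13 | 0.15 |
| 80 | 0.11 | 0.14 |
| 60 | 0.08 (15% of fits fail) | 0.12 (2% fail) |
| 50 | 0.06 (38% fail) | 0.11 (8% fail) |

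Exposure-only and Firth-penalised fits gave 0.19 to 0.20 throughout. The bias is real if that model was fitted.

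**3. Likely discordant counts.** The documents do not report them, so these are assumptions. Control prevalences from Table 10 are 209/238, 145/228 and 110/228. The MI cells are misplaced in that table; 228 − 118 = 110 controls with MI gives (23 × 118)/(205 × 110) = 0.12, the printed crude odds ratio. Applying the unmatched adjusted odds ratios (0.13, 0.13, 0.26) gives treated prevalences of 0.484, 0.185 and 0.195. With outcomes independent within pairs, the discordant share is p0(1 − p1) + p1(1 − p0):

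- Dysmenorrhea: 98 × 0.512 = 50
- PMS: 98 × 0.586 = 57
- MI: 98 × 0.489 = 48

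**4. Printed precision against a full-list fit.** The standard error implied by Table 11 is ln(upper/lower)/3.92. The simulated columns take the unmatched adjusted odds ratio as the truth.

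| Outcome | Printed OR, SE | Full list at assumed count | Full list, all 98 discordant |
|---|---|---|---|
| Dysmenorrhea | 0.13, ln(0.34/0.05)/3.92 = 0.49 | 0.03, SE 1.30 | 0.06, SE 0.57 |
| PMS | 0.12, ln(0.27/0.06)/3.92 = 0.38 | 0.05, SE 0.79 | 0.08, SE 0.45 |
| MI | 0.21, ln(0.45/0.09)/3.92 = 0.41 | 0.15, SE 0.56 | 0.21, SE 0.30 |

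At the assumed counts, only 2%, 0.5% and 10% of converged full-list fits had a standard error as small as the printed one. In repeat runs, 63% to 66% of the dysmenorrhea fits failed outright, so its 0.03 and 1.30 describe a selected minority.

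**5. Exposure-only fit.** Here OR = b/c and SE = √(1/b + 1/c), with b and c the two discordant counts. With a normal quantile, 7 vs 57 reproduces the PMS row. No split matches the other two exactly: 5 vs 37 gives 0.135 (0.053, 0.344) for dysmenorrhea, so both limits match and the estimate is just over the rounding boundary. With a t quantile on b + c − 1 degrees of freedom, all three rows are reproduced:

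- Dysmenorrhea, 5 vs 38: SE = √(1/5 + 1/38) = 0.476; 0.13 (0.05, 0.34)
- PMS, 7 vs 57: SE = 0.400; 0.12 (0.06, 0.27)
- MI, 8 vs 39: SE = 0.388; 0.21 (0.09, 0.45)

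The totals are 43, 64 and 47 discordant pairs, near the 50, 57 and 48 of step 3.

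**6. Matched against unmatched.** The adjusted odds ratios before and after matching are 0.13 and 0.13, 0.13 and 0.12, and 0.26 and 0.21. Inflation of the size in step 4 is not visible for dysmenorrhea or PMS.

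**The case for a change.** The strongest counter-argument is that this is the primary analysis and its terms should not have to be inferred. Table 11 separates crude from adjusted odds ratios and puts the matched column under the adjusted label. The dysmenorrhea sentence speaks of regression models without exception, and the opposing reading is partly an inference from silence. The match in step 5 was found after trying seven interval methods, so it shows that exposure-only is possible, not that it was fitted. For MI, a full-list fit with more discordant pairs than assumed could also give the printed precision.

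These points stand, but they show only that the text is incomplete. The adjusted label is also natural for an estimate from a sample matched on covariates. A penalised likelihood would answer a problem in a model that nobody has shown was used; exposure-only and a shorter list are equally defensible. Nor are they interchangeable with a full-list estimate: if every covariate had a log odds ratio of 0.4 in size (an assumption), a covariate-conditional 0.20 would correspond to an exposure-only value of about 0.24 to 0.27.

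**Conclusion.** The gap is real but narrow: the covariates are named, yet no section ties either list to the conditional model, and the discordant-pair counts are not reported. The harm depends on a full-list fit by ordinary conditional likelihood, and the printed results lean against that. Table 11 implies standard errors of 0.49, 0.38 and 0.41, against about 1.3, 0.8 and 0.6 for a full-list fit at the assumed counts, and an exposure-only fit can reproduce every row. The case is reasonably strong for dysmenorrhea and PMS and open for MI. It rests on the assumed discordant counts, on independence within pairs and on covariates without effect on the outcome in the simulation; the unmatched odds ratios used as a benchmark have wide intervals and come from a different sample. This is a detail of specification left to the analysts and apparently handled sensibly. No change to the analysis follows.

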Combined Document: Study Protocol, Statistical Analysis

Plan (SAP), and Informed Consent Form (ICF)

Official Title of the study: Behavioral change communication intervention in menstrual disorder management among female university students in Bangladesh

[name]. [name]

Principal investigator of the study

Shahjalal University of Science and Technology (SUST), Sylhet, Bangladesh

Document date: 26 May 2025

Approved by the SUST Research Ethics Board (Ref: AST/002/258)

Study Protocol

Brief summary

Menstrual health is a neglected area of women's health research, especially in low- and middle-income countries, despite the high prevalence and impact of menstrual disorders on daily life. These issues are particularly common among young women in academic settings, yet few interventions address them holistically. In Bangladesh, female university students frequently experience dysmenorrhea, premenstrual syndrome (PMS), and menstrual irregularity (MI), conditions often worsened by modifiable lifestyle factors such as poor diet, physical inactivity, and food cravings. This study assessed the effectiveness of Behavior Change Communication (BCC) intervention promoting non-pharmacological strategies to improve menstrual health among female university students.

A quasi-experimental design included 498 participants (249 per group), aged 19–25, from three public universities. The intervention group received three interactive BCC sessions on menstrual disorders, diet, and physical activity (including yoga) between May and June 2023, followed by bi-monthly visits for six months. Post-intervention data were collected from February to March 2024. Outcomes (dysmenorrhea, PMS, MI) were measured using validated tools. Propensity score matching (1:1 nearest-neighbor, caliper = 0.01) yielded 98 matched participants per group. Covariates included physical activity, body mass index (BMI), dietary diversity, food cravings, breakfast skipping, sleep, bedtime, caffeine intake, and socio-demographic factors. Data were collected via validated Bengali questionnaires. Analyses included descriptive statistics, chi-square and t-tests, logistic regression, and sensitivity analyses. Ethical approval was granted by the Shahjalal University Ethics Board.

Detailed description of the study

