Outcome	Group	Overall number of baseline participants	Baseline analysis population description
Dysmenorrhea	Intervention	234	After recruitment and data quality checks, 234 participants were included in the initial analysis. After propensity score matching, 98 were retained.
	Control	238	From 238 eligible controls, 98 matched participants were used in the final matched analysis.
	Total	472	The final matched sample included 196 participants (98 per group), selected through 1:1 propensity score matching without replacement using a caliper of 0.01.
PMS and MI	Intervention	228	228 participants provided valid and complete responses and were included in the baseline analysis. After matching, 98 were included in the final matched analysis.
	Control	228	228 participants were eligible for baseline analysis. After matching, 98 were used for final analysis.
	Total	456	A total of 196 participants (98 in each group) were retained after 1:1 matching with a 0.01 caliper and no replacement.

Baseline Measure Information

The baseline characteristics of study participants were assessed using a combination of study-specific and standard measures to comprehensively capture their lifestyle, nutritional, reproductive, and socio-demographic profiles (Table 6). Study-specific measures included

physical activity level (categorized according to WHO guidelines), body mass index (BMI) using Asian-specific cut-offs, and minimum dietary diversity (MDD) based on a 5-day food diary aligned with FAO recommendations. Additional lifestyle factors assessed included food cravings, skipping breakfast, sleep duration, caffeine intake frequency, and bedtime. Reproductive health and demographic factors such as age, age at menarche, marital status, and participant's residence, family history of menstrual disorders, as well as parental education and occupation were also recorded. These baseline measures were used to describe the participant population and to adjust for potential confounding in subsequent analyses.

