Dietary diversity Score (DDS)	MDD (scoring ≥ 5)	Dietary diversity was assessed using a 5-day food diary based on the 24-hour recall method, following FAO guidelines. Food items were classified into 10 predefined groups, and scores ranged from 0 to 10. Minimum dietary diversity (MDD) was defined as achieving a score of 5 or more.	Count of participants	Not applicable	Yes / No	Participants
Food Craving	Food craving for high-fat and sweet food	Self-reported craving for high-fat and sweet food.	Count of participants	Not applicable	Yes / No	Participants
Skipping breakfast	Skipping breakfast	Reported skipping breakfast one or more times during the last week.	Count of participants	Not applicable	Yes / No	Participants
Sleep duration	Sleep hours per night	Based on self-reported average nightly sleep duration	Count of participants	Not applicable	<7 hrs / ≥7 hrs	Participants
Caffeine consumption	Frequency of caffeine Intake	Based on frequency of caffeine intake per week; categorized as infrequent (<3 times/week) or frequent (≥3 times/week)	Count of participants	Not applicable	Infrequent / Frequent	Participants

Bedtime	Bedtime (hours)	Bedtime was classified into two groups: ≤23:00 hours and >23:00 hours, based on a 24-hour clock format	Count of participants	Not applicable	Before or at 23:00 / After 23:00	Participants
Family history of menstrual disorders	Family history of menstrual disorders	Participants reported whether they had family history of any kind of menstrual disorders viz. dysmenorrhea, PMS, or IMC.	Count of participants	Not applicable	Yes / No	Participants
Age (Not study-specific measure)	Age	Treated as continuous variable	Mean	Standard deviation	Not applicable	Participants
Menarche age	Age at menarche	Reported age at first menstruation in years and treated as continuous variable.	Mean	Standard deviation	Not applicable	Participants
Marital status	Marital status	Marital status was self-reported. Participants categorized as divorced, separated, or recently married were grouped under ever married. All others were classified as never married.	Count of participants	Not applicable	Never married / Ever married	Years
Residence	Participant's residence	Living arrangement of the participants during the study time.	Count of participants	Not applicable	With Family / at student dormitory	Participants

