Father's Education	Father's educational status	Education levels were categorized as: "Below secondary education" (no formal education, primary, or incomplete secondary schooling) and "Secondary or higher education" (completed secondary school, higher secondary, college, or university)	Count of participants	Not applicable	Below Secondary (0-5 y schooling) / Secondary and above(> 5 y schooling)	Participants
Mother's Education	Mother's educational status					
Father's Occupation	Father's occupational status	Occupational status was self-reported as either Formal (salaried or secure jobs) or Informal (homemaking, daily wage, or insecure work)	Count of participants	Not applicable	Formal / Informal	Participants
Mother's Occupation	Mother's occupational status					

Number of baseline participants

The number of baseline participants is the same as the overall number of baseline participants, as it includes all individuals who completed baseline data collection and met the data quality criteria.

Although PSM was later used to create comparable groups for outcome analysis, the baseline measures reflect the entire recruited sample before matching. Therefore, no separate or reduced sample size is reported in this section.

Baseline Measure Data

Baseline characteristics were assessed at the time of outcome evaluation for both the intervention and control groups. Although data were collected post-intervention, propensity score matching was applied to balance pre-existing covariates and reduce selection bias in estimating the treatment effect. The Table 7(A and B) present the baseline values for each measure across the intervention and control groups, as well as for the total study population.

Table 7A. Comparison of baseline characteristics between study groups for dysmenorrhea outcome

Variables	Control (n = 238)	Intervention (n = 234)	Total (N = 472)
Physical activity level			
Sedentary	206 (43.6)	114 (24.2)	320 (67.8)
Active and Athlete	32 (6.6)	120 (25.6)	152 (32.2)
BMI (kg/m²)			
Normal weight (18.5-22.9)	83 (17.6)	171 (36.2)	254 (53.8)
Underweight (<18.5)	44 (9.3)	37 (7.8)	81 (17.2)
Overweight and obese (>22.9)	111 (23.5)	26 (5.5)	137 (29.0)
MDD (scoring ≥ 5)			
No	153 (32.4)	96 (20.3)	249 (52.8)
Yes	85 (18.01)	138 (29.2)	223 (47.2)
Food craving for high fat and sweet food			
No	77 (16.3)	164 (34.8)	241 (51.1)

Yes	161 (34.1)	70 (14.8)	231 (48.9)
Skipping breakfast			
No	72 (15.5)	169 (35.8)	241 (51.1)

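### Age is in neither stated covariate list, the PMS/MI list also drops five background variables kept for dysmenorrhea, and no propensity-model list or post-match balance figure shows whether this matters

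*Combined protocol and SAP*

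**What the plan says.** Table 6 defines 17 variables: physical activity, BMI, dietary diversity, food craving, breakfast skipping, sleep duration, caffeine, bedtime, family history, age, age at menarche, marital status, residence, and education and occupation of each parent.

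The covariates are described in four places.

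- **Baseline Measure Information, general text.** After naming the recorded variables, age among them: "These baseline measures were used to describe the participant population and to adjust for potential confounding in subsequent analyses".
- **Baseline Measure Information, dysmenorrhea.** A named list that closes with "These balanced covariates (13 covariates) were included in the regression models" and says the same set served the ATE and ATT.
- **Baseline Measure Information, PMS and MI.** A shorter named list that closes with "These variables (8 covariates) were subsequently adjusted for in the estimation of treatment effects".
- **Brief summary and Detailed description.** Broader sets, tied to no particular model. The Brief summary ends its list with "breakfast skipping, sleep, bedtime, caffeine intake, and socio-demographic factors". The Detailed description has "skipping breakfast, sleep duration, bedtime and caffeine intake" among the lifestyle covariates, then "Socio-demographic variables included family history of menstrual disorders, age at menarche, marital status", followed by residence and parental education and occupation. It does not name age as a covariate.

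The SAP (Statistical analysis overview; Other statistical analysis) says the propensity score came from logistic regression and that balance was checked against a 10% SMD limit, variance ratios and density plots. It lists no propensity-model covariates and gives no post-match value. Tables 7A and 7B show the sample before matching. The statements that the 98 pairs were balanced on key covariates carry no figures.

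**The concern.** Women in the intervention group registered voluntarily, while controls were drawn from dormitory records. Without randomization, adjustment for recorded background variables is the main measured protection against selection bias. A background variable that differs between groups, predicts the outcome and is left out can distort the odds ratio, the ATE and the ATT together. If the stated lists are what was used, agreement between Tables 11 and 12 would not reveal an omission common to all of those estimates.

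Age is the plainest case: it was recorded, it differs between groups, and the sessions cannot change it. The PMS/MI list raises a second question. It drops variables that the study treated as key covariates for dysmenorrhea in almost the same women. Table 6 defines family history to cover PMS and irregular cycles as well as dysmenorrhea, so by the study's own definition it concerns the outcomes from which it is dropped.

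The section Limitation and caveats mentions residual confounding from lack of randomization in general terms, and control-group confounders that were not assessed. It does not say that recorded, imbalanced variables lie outside the stated adjustment.

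**Working it through.** **1. The lists.** The names given add up to the stated counts, so both lists are closed.

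- Dysmenorrhea: 13 named. Absent: 17 − 13 = 4 (age, bedtime, residence, father's occupation).
- PMS/MI: 8 named. Absent: 17 − 8 = 9 (age, bedtime, caffeine, family history, marital status, education of each parent, occupation of each parent).

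**2. Imbalance before matching.** Inputs are the counts, means and SDs in Tables 7A (238 control, 234 intervention) and 7B (228 each).

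- Proportions: SMD = |p0 − p1| / √[(p0(1 − p0) + p1(1 − p1))/2].
- Age: SMD = difference in means / √[(SD0² + SD1²)/2].

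Age, dysmenorrhea sample: (21.9 − 21.0) / √[(1.4² + 1.5²)/2] = 0.9/1.451 = 0.62. Moving each mean and SD by up to 0.05 for rounding gives 0.53 to 0.71.

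Age, PMS/MI sample: (22.0 − 21.0)/1.451 = 0.69, with a rounding range of 0.60 to 0.79.

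Family history, PMS/MI sample: p0 = 77/228 = 0.338 and p1 = 37/228 = 0.162. The SMD is 0.175/√[(0.2237 + 0.1359)/2] = 0.175/0.424 = 0.41.

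The same formula gives the rest (control vs intervention counts):

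| Variable | 7A counts | 7A SMD | In dysmenorrhea list? | 7B counts | 7B SMD | In PMS/MI list? |
|---|---|---|---|---|---|---|
| Age | see above | 0.62 | no | see above | 0.69 | no |
| Family history, yes | 78 vs 37 | 0.40 | yes | 77 vs 37 | 0.41 | no |
| Father below secondary | 50 vs 17 | 0.40 | yes | 48 vs 16 | 0.41 | no |
| Ever married | 22 vs 8 | 0.24 | yes | 22 vs 7 | 0.27 | no |
| Mother below secondary | 62 vs 39 | 0.23 | yes | 60 vs 37 | 0.25 | no |
| Mother's occupation formal | 66 vs 44 | 0.21 | yes | 65 vs 44 | 0.22–0.23 | no |
| Residence with family | 18 vs 46 | 0.36 | no | 17 vs 44 | 0.35 | yes |
| Father's occupation formal | 138 vs 144 | 0.07 | no | 130 vs 142 | 0.11 | no |
| Frequent caffeine | 173 vs 77 | 0.87 | yes | 168 vs 76 | 0.88 | no |
| Bedtime by 23:00 | 26 vs 139 | 1.18 | no | 24 vs 137 | 1.21 | no |

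The range for mother's occupation in 7B arises because the intervention cells sum to 44 + 185 = 229, not 228. Using 44/228, 44/229 or 43/228 gives 0.217, 0.219 or 0.228.

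**3. What the comparison shows.** The imbalance of the five background variables is nearly the same in the two samples, so lack of imbalance cannot explain why the PMS/MI list drops them. Residence runs the other way, again at equal imbalance.

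**4. What cannot be computed.** The documents give no matched-sample covariate data and no covariate–outcome associations. Neither the post-match SMDs nor the size of any bias can be derived.

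**5. Room for extra terms in the primary model.** Conditional logistic regression uses only pairs with discordant outcomes, and their number is not reported. As an illustration, assume that the ATT in Table 12 and the matched OR in Table 11 describe the same 98 pairs, and ignore covariate adjustment. Then discordant pairs = 98 × |ATT| × (1 + OR)/(1 − OR).

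- Dysmenorrhea: 98 × 0.27 × 1.13/0.87 ≈ 34.
- PMS: 98 × 0.42 × 1.12/0.88 ≈ 52.
- MI: 98 × 0.31 × 1.21/0.79 ≈ 47.

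With BMI as two terms, the dysmenorrhea model with age would have 14 + 1 (intervention) + 1 = 16 parameters. The PMS/MI model with age, family history, both parents' education and mother's occupation would have 9 + 1 + 5 = 15.

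**The case against.** The best defence is that this is a gap in reporting and not a demonstrated error of analysis. The word balanced may mean that the lists hold only the variables that reached balance, so the propensity model may have been larger. The general sentence in Baseline Measure Information says that the recorded measures, age included, were used for adjustment. Matching on other variables may also have brought age into balance. Choosing covariates by outcome is accepted practice. Participants were aged 19 to 25, and the age SMD is large partly because the SD is only about 1.5 years.

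Much of this stands. The 10% limit applies after matching, the SMDs above are before matching, and none of the variables is shown to be a confounder. Different lists are not in themselves wrong; the fault is that no reason is given. But the general sentence does not show that age entered any model, and it conflicts with two lists closed by their own counts.

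Two stronger readings are tempting. A reader might infer that age and the other variables were left out of the propensity model and that the results are biased; the documents do not say so. A reader might also point to bedtime and caffeine, which have the largest gaps, or quote 4 of 17 and 9 of 17 as counts of omitted confounders. The documents do not support that either. "Baseline characteristics were assessed at the time of outcome evaluation for both the intervention and control groups", so bedtime and caffeine may have been changed by the sessions, and adjusting for them could remove part of the effect. Father's occupation was near balance even before matching. These three need a stated reason, but they are not evidence of omitted confounding.

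**Conclusion.** The point holds as an unexplained inconsistency in the stated adjustment, together with missing balance figures. Age is absent from both lists (pre-match SMD 0.62 and 0.69). Five background variables are absent for PMS/MI only (0.22 to 0.41), and residence for dysmenorrhea only (0.36). These figures rest on Tables 7A and 7B as printed and on reading the two counted lists as complete. Whether the variables were in the propensity model, and whether they were balanced in the 98 pairs, cannot be told from the documents. Bias in the reported effects is possible, but neither its presence nor its size is shown. This should be corrected; it does not by itself overturn the results.

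**What to change.** 1. List the covariates of each propensity model and each outcome model. Reconcile the Detailed description with the general sentence and the two counted lists in Baseline Measure Information. Give the reason for each omission, including bedtime, caffeine and father's occupation.
2. Report post-match SMDs for all 17 variables in the current pairs, for each matched sample.
3. If age was not in the propensity model, add it for all three outcomes. For PMS/MI, add family history, parental education and mother's occupation where the post-match SMD exceeds 10%. Treat marital status (PMS/MI) and residence (dysmenorrhea) the same way only if they can be taken as pre-exposure: ever married includes women recently married, and residence refers to the study period. Family history needs a note, since "Participants reported whether they had family history of any kind of menstrual disorders" and, as with the other baseline measures, this was collected after the sessions, so reporting may differ by group.
4. Prefer adding variables to the propensity model and re-matching over adding many terms to the conditional logistic model.
5. Results already exist, so report any re-analysis beside them as a labelled post hoc sensitivity analysis.

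Cost: items 1 and 2 need no new data and no re-matching. Re-matching may lose an unknown number of pairs and widen the intervals. Adding many terms to the conditional model risks sparse-data bias, given perhaps 34 to 52 discordant pairs on the illustration above.
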